9.2. NYHA FUNCTIONAL CLASS

NYHA functional class will be assessed at Screening, Baseline, Week 2 and Months 1, 2, 4 and every 4 months thereafter.

NYHA Functional Class will be summarized categorically at each Visit (Week 2 and Months, 2, 4, 8 and 12). A shift table for changes from baseline will also be presented.

The proportion of subjects who improve their functional class will be estimated for each group at each visit (Week 2 and Months 2, 4, 8 and 12) along with its 95% 2-sided binomial confidence interval. Those subjects who didn't have the potential to reach the visit will be taken as missing, but those who withdrew will be taken as not improving.

9.3. NT-proBNP

NT-proBNP will be assessed at Screening, Baseline, Week 2 and Months 1, 2, 4 and every 4 months thereafter.

Values and changes from baseline will be summarized by visit (Week 2 and Months 2, 4 and 8). Geometric means will be included for the absolute values and the ratio to baseline from back-transforming the mean changes from baseline for natural log data will be presented for the changes from baseline. The 95% confidence intervals will also be presented for the ratios. The ratios and 95% CIs will be plotted against visit for each group.

Values and changes from changes from baseline will also be summarized for the age sub-groups (<75 years of age and \geq 75 years of age).

The change from baseline in NT-proBNP to Month 8 will be analyzed using an MMRM analysis with group, visit and group-by-visit interaction as fixed effects and baseline as a covariate. An unstructured covariance will be attempted, but alternative structures will be explored if the unstructured structure isn't suitable. The Kenward-Roger method will be used to adjust the degrees of freedom. Comparisons of the least square means for the interaction term, group by visit, will provide inferential statistics for comparisons between groups at Months 2, 4 and 8. Given that the data are skewed with some subjects having very high values, a natural log transformation will be applied to the data prior to analysis. Consequently back-transformed LS means will provide ratio comparisons of the groups.

9.4. MLWHF QUALITY OF LIFE QUESTIONNAIRE

The MLWHF Quality of Life Questionnaire will be assessed at Baseline, Month 2, Month 4 and every 12 months thereafter. The Questionnaire has 21 items, each scored within the range 0 to 5. Two domains and 1 total score will be derived:

- Physical Dimension (Range 0 to 40)
- Emotional dimension (Range 0 to 25)
- Total Score (Range 0 to 105)

Higher scores denote poorer quality of life. The scores are provided by the site in the eCRF. The scores will be used as provided, even if answers to some of the individual questions are missing.

Scores and changes from baseline will be summarized by visit (Months 2, 4 and 8).

The changes from baseline to Month 8 will be analyzed using an MMRM analysis with group, visit and group-by-visit interaction as fixed effects and baseline as a covariate. An unstructured covariance will be attempted, but alternative structures will be explored if the unstructured structure isn't suitable. The Kenward-Roger method will be used to adjust the degrees of freedom. Comparisons of the least square means for the interaction term, group-by-visit, will provide inferential statistics for comparisons between groups at Months 2, 4 and 8.

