6.2. MISSING DATA

All possible efforts will be made to minimize missing data. No imputation of missing data will be performed unless specifically mentioned.

The original data will always be presented in the listings.

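### MLWHF scores from incomplete forms are taken unadjusted, so blank items can lower a score and scoring may differ between sites

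*SAP*

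**What the plan says.** SAP section 9.4 describes the instrument: "The Questionnaire has 21 items, each scored within the range 0 to 5". It defines a physical score of 0 to 40, an emotional score of 0 to 25 and a total of 0 to 105, and gives the direction: "Higher scores denote poorer quality of life". On the source of the scores it says "The scores are provided by the site in the eCRF", and on incomplete forms "The scores will be used as provided, even if answers to some of the individual questions are missing". The scores and their changes from baseline are summarised by visit. The changes then go into a repeated-measures model that compares Transition with Add-On, with baseline as a covariate.

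The general rule in SAP section 6.2 is "No imputation of missing data will be performed unless specifically mentioned". Nothing is mentioned for MLWHF items. Neither document gives a minimum number of answered items, a proration rule, a rule for setting an incomplete score to missing, or a sensitivity analysis. Protocol section 6.10 sets only when the questionnaire is given.

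**The concern.** This is a stated rule for incomplete forms, not a silence. If a score is a sum and high is bad, a blank that is passed over in the addition has the same effect as the best possible answer. The model cannot repair this. It accommodates visits with no score, but it treats an understated score as fully observed.

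The rule also differs in spirit from the rest of the SAP. Section 6.2.2 gives adverse events with missing causality, seriousness or severity the least favourable category. Section 9.2 counts withdrawn subjects as not improved in functional class. In MLWHF, a gap can make the patient look better at that visit.

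At stake is how the MLWHF summaries and the between-group comparison are read. All patients receive open-label LIQ861, so no control arm offsets an error in the within-group changes. The protocol allows up to 50 sites, which leaves room for different scoring habits.

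**Working it through.** **1. Do the stated ranges fit plain sums?** Inputs from SAP 9.4: 21 items, each 0 to 5.

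- Total: 21 × 5 = 105, which matches the stated maximum.
- Physical: 40 / 5 = 8 items. Emotional: 25 / 5 = 5 items. The other 21 − 8 − 5 = 8 items count only in the total.

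The ranges fit sums for a complete form. They do not show what a site does with an incomplete one.

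**2. Effect on one form, if the site adds only the answered items.** With *m* blanks whose true mean is *x*, the score is too low by *m* × *x*. The documents give no item means, so *x* = 1 to 3 is assumed (totals of 21 to 63).

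| Blanks | *x* = 1 | *x* = 2 | *x* = 3 |
|---|---|---|---|
| 1 | −1 | −2 | −3 |
| 2 | −2 | −4 | −6 |
| 3 | −3 | −6 | −9 |

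The limit is 5 points per blank. For a domain score that is up to 5/40 = 12.5% of the physical range or 5/25 = 20% of the emotional range.

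**3. Effect on change from baseline.** Take no true change, *x* = 2 and three blanks. The full score is 21 × 2 = 42 and the summed score is 18 × 2 = 36.

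- Blanks only after baseline: 36 − 42 = −6, a false improvement.
- Blanks only at baseline: 42 − 36 = +6, a false worsening.
- The same blanks at both visits: 36 − 36 = 0.

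**4. Effect on a group mean.** If a fraction *f* of forms lack *m* items and all are summed, the mean score at that visit shifts by −*f* × *m* × *x*. The documents give no *f* or *m*, so both are assumed.

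- *f* = 10%, *m* = 2: −0.2, −0.4 and −0.6 for *x* = 1, 2 and 3.
- *f* = 20%, *m* = 4: −0.8, −1.6 and −2.4.

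**5. Effect on Transition versus Add-On.** The same shift in both groups drops out of the difference. What remains is the difference between the groups' shifts, so it is zero unless skipping or site scoring differs between them.

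**6. What proration does.** The prorated total is the raw sum × 21 / (21 − *m*). With *x* = 2 and three blanks, 36 × 21 / 18 = 42, the full score. This recovery is exact only if the blank items average the same as the answered ones.

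**The case against.** The strongest reply is that the SAP never calls the score a sum and never says that blanks count as zero. A site might prorate before entry, leave the score empty, or follow scoring instructions that these documents do not include. A site that prorated would not create this bias. This stands. A reader might infer that the SAP has adopted zero imputation as its rule, but the text supports less: an unadjusted score is accepted without any stated method for blanks.

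Second, a reader might infer that MLWHF results are biased toward improvement. The documents do not support that either. The endpoint is a change from baseline, its direction depends on which visit has more blanks, and nothing indicates more skipping after baseline. Equal skipping largely cancels, both over time and between groups.

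Third, the several-point effects in step 2 belong to a single form and should not be read as shifts in a reported mean.

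Fourth, the endpoint is exploratory. Protocol section 6.1.2 disclaims efficacy conclusions and section 8.4 plans no formal testing. The SAP is also open about its rule and lists the original data. This limits the weight of the point but does not make the rule a good one: under it, the analyst applies no correction whichever method a site used.

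Finally, central rescoring needs item answers, and the SAP confirms only that scores are in the eCRF. Its reference to missing individual answers suggests that completeness can be known, but does not prove it. The fix therefore needs a fallback.

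**Conclusion.** The point holds as a weakness in an exploratory analysis. Scores from incomplete forms enter unadjusted. Where a site has added up such a form, that visit's score is too low by the true value of the skipped items. Where sites use different methods, the scores are not comparable.

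The net effect on the reported changes is unknown in size and direction, because the documents give neither a rate of missing items nor a site scoring method. With 10% of forms lacking two items, item means of 1 to 3 and simple summing, all assumed, the mean score at that visit falls by 0.2 to 0.6 points. It could be larger with more blanks, or nil if forms are complete or already prorated. The between-group comparison is distorted only by differential skipping or scoring. The primary safety result is not touched.

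**What to change.** Replace the rule in SAP section 9.4 with the following:

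- Where item answers are in the eCRF, derive both domain scores and the total centrally. If at least half of a scale's items are answered (4 of 8 physical, 3 of 5 emotional, 11 of 21 total), multiply the mean of the answered items by the number of items in the scale. Otherwise set that score to missing.
- Where items are not held but the form is flagged as incomplete, exclude that score in a sensitivity table.
- Report the number of incomplete forms by visit and group. If there are few, this table alone shows that the choice hardly matters.

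The half-scale threshold is a proposal, not something taken from the documents. What matters is that one rule is fixed in advance and applied to every site.

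The cost is a short SAP amendment, which SAP section 2 allows before database lock, and a little programming. A few scores become missing. Because data through Month 2 have been reported, Month 2 MLWHF values may differ slightly from any already published in that report, and the CSR should note this.

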6.2.6. Visits 6+ (Month 4)

6.2.6.1. In Clinic at Month 4 and Every 4 Months thereafter until Study Termination Visit

Visit 6 should be scheduled approximately 4 months \pm 7 days from the first administration of LIQ861 and in-clinic follow-up visits should be scheduled every 4 months \pm 7 days thereafter.

The following assessments may be done before or after study drug administration at Visit 6 and all subsequent in clinic follow-up visits:

- Full Physical Examination (at Visit 6 and every 12 months thereafter)
- NYHA Functional Class Assessment
- Collect unused study drug
- Study drug accountability
- Assess PAH Symptoms
- Consider dosing adjustments and record any prescribed changes
- Study drug dispensation
- Schedule next visit
- Schedule telephone follow-up visit for 8 weeks from the current visit to assess AEs, concomitant medications, PAH symptoms, and dose adjustment.

The following assessments will be conducted prior to study drug administration at Visit 6 and all subsequent in clinic follow-up visits:

- Vital signs (temperature, blood pressure, respiratory rate, and heart rate) collected after the patient has been upright and rested for at least 5 minutes (at Visit 6 and every 12 months thereafter)
- Weight (at Visit 6 and every 12 months thereafter)
- Venous blood for clinical laboratory tests
 - NT-proBNP collected at every 4 month visit
 - Hematology and Blood Chemistry collected at Visit 6 and every 12 months thereafter
- DPI re-training
- Concomitant medications
- Treatment-Emergent Adverse Events
- Record time of last dose of inhaled treprostinil
- Administration of study drug
 - Note that the time of LIQ861 administration should be at least 4 hours after the last dose of LIQ861

The following assessments will be conducted after study drug administration at Visit 6 and all subsequent in clinic follow-up visits:

- 6MWT (within 15 to 60 minutes after administration of LIQ861)
- Inhalation Device User Survey (at Visit 6 and every 12 months thereafter)
 - The Inhalation Device User Survey should only be administered to Tyvaso Transition patients.
- MLWHF questionnaire (at Visit 6 and every 12 months thereafter)
- Concomitant medications

- Treatment-Emergent Adverse Events

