6.2.6.3. Study Termination Visit

Study termination visits will occur when a patient is discontinued from the study or once the Sponsor has decided to terminate the study.

The following assessments should be conducted during the Study Termination Visit:

- Full Physical Examination
- Weight and height
- Vital Signs (temperature, blood pressure, respiratory rate, and heart rate) collected after the patient has been upright and rested for at least 5 minutes
- Venous blood for clinical laboratory tests, including NT-proBNP
- 6MWT
- NYHA Functional Class Assessment
- Assess PAH Symptoms
- Inhalation Device User Survey
 - The Inhalation Device User Survey should only be administered to Tyvaso Transition patients.
- MLWHF questionnaire
- Record time of last dose of LIQ861
- Treatment-Emergent Adverse Events
- Concomitant medications
- Collect unused study drug
- Study drug accountability

At the Study Termination Visit, Study Drug Dispensation will not be performed and future visits should only be scheduled for follow-up visits in the event of an Early Termination. All remaining supply of Study Drug should be collected and reconciled.

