6.10. Patient Questionnaires

For all patients, the MLWHF questionnaire ([Rector and Cohn 1992](#)) will be administered at Baseline (Day 1), Visit 5 (Month 2), Visit 6 (Month 4), and every 12 months thereafter.

For all Tyvaso Transition patients, responses to the Inhalation Device User Survey ([Appendix 5](#)) will be collected at Baseline (Day 1), Visit 3 (Week 2), Visit 6 (Month 4), and every 12 months thereafter.

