6.2.5. SUMMARY TABLE PRESENTATIONS

In summaries for continuous data, the number of missing values will be presented. The missing count will not include subjects who have discontinued at earlier visits or not had the potential to reach the visit (i.e. subject transitioned to extension study prior to reaching the visit).

In summaries for categorical data the following categories will be included:

- No potential to reach the visit
- Withdrew prior to the visit
- Missing

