6.4. VISIT WINDOWS

Data will be assigned to visits using windowing (see table below). If more than one assessment (including the early termination or unscheduled assessments) falls within the same defined window, the assessment closest to the target day with non-missing data will be considered for analysis; however, with the exception of laboratory and vital sign data, the visit must be within 7 days of the final dose of study treatment. For laboratory and vital sign data the assessment must be no more than 1 day after the final dose of study treatment. If two qualifying assessment dates are at the same distance from the target day, the latest assessment with non-missing data will be taken for analysis.

Visit	Target Day	Analysis Window	Interval
Baseline ^a	1 ^b	Day -30 to Day 1	
Week 2	14	2 -22	21
Month 1	30	23 – 45	23
Month 2	60	46 – 90	45

Visit	Target Day	Analysis Window	Interval
Month 4	120	91 – 150	60
Month 8	240	211 – 270	60
Month 12	360	331 – 390	60
Month 16	480	451 – 510	60
Month m	30m	(30m - 29) – (30m + 30)	60

^a Baseline is the last assessment taken prior to the start of study treatment.

^b Day 1 represents the first day of study treatment.

Please note that telephone visits are not included as only log data will be collected at those visits (e.g. AEs and concomitant medications).

These visit windows will be reviewed and may be updated prior to reporting. Any assessments that fall outside of these windows will be reviewed on a case-by-case basis, and decisions on their handling will be fully documented prior to reporting. Data collected outside these windows will only be listed.

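### SAP 9.4 compares groups on MLWHF at Month 8, when no MLWHF form is due, and SAP 9.5 tabulates the device survey at Month 2, when no survey is due

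*SAP*

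**What the plan says.** **MLWHF, collection.** SAP 9.4 opens by saying that the questionnaire "will be assessed at Baseline, Month 2, Month 4 and every 12 months thereafter". Protocol 6.10 agrees: it "will be administered at Baseline (Day 1), Visit 5 (Month 2), Visit 6 (Month 4), and every 12 months thereafter". So does the visit list in Protocol 6.2.6.1: "MLWHF questionnaire (at Visit 6 and every 12 months thereafter". Protocol 3.2.4, footnote f of the main schedule in Protocol Appendix 1, and the endpoint list in SAP 4.4 follow the same pattern. The only other collection point is the Study Termination Visit (Protocol 6.2.6.3).

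**MLWHF, analysis.** The same SAP section then states "Scores and changes from baseline will be summarized by visit (Months 2, 4 and 8". It fits a mixed model for repeated measures (MMRM) to change from baseline up to Month 8, and says that the group-by-visit least squares means "will provide inferential statistics for comparisons between groups at Months 2, 4 and 8".

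**Device survey.** Protocol 6.10 and SAP 9.5 both place post-baseline surveys at Week 2, Month 4 and yearly after that; the Study Termination Visit adds one. The Month 1 and Month 2 procedures in Protocol 6.2.5 do not include it. SAP 9.5 nevertheless plans response tables for Months 2 and 4.

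**The concern.** The analysis visits do not match the collection visits. The affected cells need not be empty, and that is what makes them misleading. SAP 6.4 assigns data to visits by day, "including the early termination or unscheduled assessments) falls within the same defined window", and the termination visit includes both instruments. As to when that visit happens, Protocol 6.2.6.3 says: "Study termination visits will occur when a patient is discontinued from the study or once the Sponsor has decided to terminate the study". Protocol 6.3 does not list MLWHF among the assessments for unscheduled visits. Having a Month 8 score therefore depends essentially on leaving LTI-301 at about that time.

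Subjects who continue on LIQ861 supply no Month 8 score. They would still be shown as missing a form that was never due, because SAP 6.2.5 removes only two kinds of subject from that count: "The missing count will not include subjects who have discontinued at earlier visits or not had the potential to reach the visit".

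A reader would take the Month 8 summary and group comparison as quality of life after eight months on treatment. They would describe withdrawals and possibly administrative leavers, in a mix that could differ between Transition and Add-On.

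**Working it through.** There is no plan figure to reproduce. The check maps due dates onto the analysis windows.

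**Inputs**
- Windows (SAP 6.4): Month 2 = Days 46–90. Month 8 = Days 211–270, which also follows from the general rule for Month m: 30×8 − 29 = 211 and 30×8 + 30 = 270.
- Visit tolerances (Protocol 6.2.4 to 6.2.6.1): Week 2 ± 2 days, Month 2 ± 3 days, Month 4 and later ± 7 days.
- Off-schedule data (SAP 6.4): early-termination and unscheduled assessments may enter a window. For data other than laboratory and vital signs, the visit must be within 7 days of the final dose.

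**MLWHF against the Month 8 window (Days 211–270)**

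| Form | Days due | Distance from window |
|---|---|---|
| Month 2 | 60 ± 3 = 57–63 | falls in the Month 2 window |
| Month 4 | 120 ± 7 = 113–127; with calendar months at most Day 124 + 7 = 131 | 211 − 131 = 80 days before |
| Next form, counted from Visit 6: Month 4 + 12 = Month 16 | from 480 − 7 = 473 | 473 − 270 = 203 days after |
| Next form, if counted by study year: Month 12 | from 360 − 7 = 353 | 353 − 270 = 83 days after |

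Periodic forms due in the Month 8 window: 0 under either reading of the yearly interval.

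**Device survey against the Month 2 window (Days 46–90)**

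| Form | Days due | Distance from window |
|---|---|---|
| Week 2 | 12–16 (target Day 14), or 13–17 if counted as 14 days after Day 1 | 46 − 17 = 29 days before |
| Month 4 | from 120 − 7 = 113 | 113 − 90 = 23 days after |

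Periodic surveys due in the Month 2 window: 0.

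**What the outputs would contain**
- *MLWHF, Month 8:* essentially only termination-visit forms dated Days 211–270 and within 7 days of the last dose. The documents do not allow that number to be calculated.
- *Survey, Month 2:* SAP 6.1 uses the analysis population as denominator. All 55 Transition subjects in the Safety Population (46 in mITT; SAP 9.5 names no population) would fall in a no-data category unless they had a termination visit on Days 46–90.

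**Comparison within the SAP.** Laboratory and vital-sign data follow the same yearly schedule after Month 4. For these, SAP 8.2 and 8.3 summarise only Months 2 and 4 plus a last on-treatment value. Month 8 also appears in SAP 9.1 to 9.3, where the assessments really are made every four months.

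**The case against.** The mismatch itself is hard to dispute; the argument is over its consequences.

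- **The MMRM keeps continuing subjects.** Their Month 2 and Month 4 scores inform the baseline slope and the covariance and, through within-subject correlation, the Month 8 means. This is true. However, the Month 8 visit and group-by-visit terms, and the covariances that link Month 8 to earlier visits, can be estimated essentially only from the forms inside the window. Borrowing strength from earlier visits does not replace Month 8 data in subjects who stayed.
- **Other sources may exist.** SAP 6.4 admits unscheduled assessments, and Protocol 6.3 does not forbid a questionnaire at such visits. Subjects moving to LTI-302, which began on 18 July 2019 (SAP 7.1), may have had termination visits. Month 8 scores could then be largely administrative and not selected on outcome. This stands as a possibility, so the direction and size of any bias are unknown. The documents do not say that roll-over subjects had a termination visit, nor that the Month 8 analysis is meant to rest on such forms.
- **The survey half looks editorial.** Week 2 is probably what was meant, and the missing category would expose the gap. A previous clinical study report covered data through Month 2, so loss of the Week 2 results is not shown. All fair, but this SAP governs final reporting and, as written, plans no Week 2 table.
- **The endpoints are exploratory** and no formal hypothesis is tested. This limits the weight of the point. SAP 9.4 still promises inferential comparisons at Month 8.

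**Conclusion.** The concern holds. No periodic MLWHF form is due in the Month 8 window and no periodic survey in the Month 2 window, whichever way the yearly interval is read. This affects one of the three MLWHF comparison visits and one of the two survey table visits.

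The schedule finding rests only on the documents' own visit days, tolerances and windows. That Month 8 scores would come essentially from leavers assumes that sites did not collect MLWHF off schedule to any real extent. How many such scores there are, how many are administrative, and whether the mix differs between groups cannot be determined from the documents.

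The MLWHF comparison is the weightier half; the survey half is minor. The plan should be corrected, but the primary safety analysis does not depend on it.

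**What to change.** **SAP 9.4.** Remove Month 8 from the descriptive summary, the MMRM and the group comparisons. Use Months 2 and 4, and keep the SAP 6.4 windowing there. Report termination-visit scores that fall outside those windows separately: in listings, or as a last on-treatment value of the kind SAP 8.2 and 8.3 already define. A descriptive Month 16 summary is optional; if wanted, state beforehand how many subjects are needed. If the sponsor did intend termination forms to supply Month 8, the SAP must say so and label the output accordingly.

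**SAP 9.5.** Change the tabulated visits from Months 2 and 4 to Week 2 and Month 4.

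**Cost.** Three sentences in SAP 9.4 and one in SAP 9.5, with no new data. SAP section 2 allows amendments until database lock.
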